Annex 7 – Data form

ETIQUETA
IDENTIFICATIVA

DATA FORM

En relació amb el pacient

Setmanes de gestació	
Tipo de preterme	
Per al néixer	
Sexe	
CPR després de néixer	
Apgar score als 5 minuts	

En relació amb la mare

Part preterme previ	
Avortament del segon trimestre	
Edat	
Alçada	
Cirurgia cervical prèvia	
Anomalia uterina congènita	
Diabetis pregestacional	
Malaltia de transmissió sexual	
Fumadora	
Consum alcohol o altres tòxics	
Període intragestacional curt	
Infecció extrauterina	

En relació amb l'embaràs

Embaràs múltiple	
Corioamnionitis	
Ruptura prematura de membranes	
Diabetis gestacional	

En relació amb la intervenció

Codi del protocol utilitzat	
Reintubació	
Temps de weaning (en dies)

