Proposed Criteria for Failure During 2 Hours on CPAP < 5 cmH₂O or T-piece

Clinical Criteria:

- Diaphoresis
- Nasal flaring
- Increasing respiratory effort
- Tachycardia (increase in HR > 40 bpm)
- Cardiac arrhythmias
- Hypotension
- Apnea

Laboratory Criteria:

- Increase of PETCO₂ > 10 mmHg
- Decrease of arterial pH < 7.32
- Decline in arterial pH > 0.07
- PaO₂ < 60mmHg with an FiO₂ > 0.40 (P/F O₂ ratio < 150)
- SpO₂ declines > 5%

Table 3 - Criteria for extubation Readiness Test Failure (56)

Invasive mechanical ventilation in RDS

Despite best efforts to maintain as many preterm babies as possible on NIV, approximately **half of babies < 28 weeks will require invasive mechanical ventilation.** (57)

The aim of invasive mechanical ventilation is to achieve “acceptable” blood gases by ventilating at optimal lung volumes (while avoiding overdistension and atelectasis).

The initial tidal volume is usually set at around 5 ml/kg (58) with a maximum PIP of 25-30 cmH₂O. Adjustments to the initial tidal volume have to be done, according to assessment of work of breathing and blood gas evolution. Required tidal volumes vary around 5-7 ml/kg, the range tending to increase with increasing postnatal age.

PEEP should be adjusted to keep the lung open by finding a point where FiO₂ is at its lowest with haemodynamic stability and acceptable blood gases.

Once stabilised on invasive mechanical ventilation and with evidence of spontaneous respiratory effort, clinicians should immediately start planning for weaning to NIV. Some infants require a very short period of ventilation, particularly those with RDS following surfactant therapy, and early extubation of even the smallest babies who achieve low ventilator settings should be encouraged. (47)

Infant's size, absence of growth restriction, oxygen requirements and blood gases can all help to determine the success of extubation. (59) Delaying extubation does not improve the chances of success.

When weaning from invasive mechanical ventilation, it is reasonable to tolerate a modest degree of hypercarbia, provided the pH remains above 7.22.

Caffeine (20 mg/kg loading, 5-10 mg/kg maintenance) should be used to facilitate weaning from MV.(60)

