7.4 Variables and measurements

Independent variable

The independent variable is the **invasive mechanical ventilation protocol** used during the weaning. It is conceived as a **dichotomous qualitative nominal variable** and is expressed as PSV/ACVGV:

- PSV: Pressure support ventilation
- ACVGV: Assist control volume guarantee ventilation

Dependent variables

There are two dependent variables: **number of reintubations** and **time of weaning**.

The **number of reintubations** is the main dependent variable. It is a **discrete quantitative variable**. The higher the number of reintubations, the higher the risk of complications, so it is a good variable to determine which protocol is more effective. Extubation failure is defined as reintubation within 24-72 hours, so the number of reintubations will be counted for the first 72 hours after the extubation.

The **time of weaning** is the secondary dependent variable. It is a **continuous quantitative variable**. It is counted from the moment the weaning is started until the extubation is executed. The longer this time is, the greater the risk of complications arising from invasive ventilation that the child may have, so it is a good variable to determine which protocol is more effective.

Covariates

- **Gestational age at birth/type of preterm:** once is born, the baby will be classified into one of these categories. It is a *dichotomous qualitative ordinal variable*:
 - Extremely preterm (< 28 weeks of gestation)
 - Very preterm (28-32 weeks of gestation)
- **Birthweight:** it is a *continuous quantitative variable* measured in grams.
- **Sex:** it is a *dichotomous qualitative nominal variable*. Categorized as men or women.
- **CPR after birth:** it is a *dichotomous qualitative nominal variable*. It will be expressed as yes or no.

- **5-minute Apgar score** (see Annex 1): It is a quantitative variable, but categorized in the following intervals, resulting in a *polychotomous qualitative ordinal variable*:
 - Apgar 0-3
 - Apgar 4-6
 - Apgar 7-10
- **Risk factors of prematurity:**
 - **Previous preterm birth:** it is a *dichotomous qualitative nominal variable*. It will be expressed as yes or no.
 - **Second trimester miscarriage (> 16 weeks):** it is a *dichotomous qualitative nominal variable*. It will be expressed as yes or no.
 - **Multiple pregnancy:** it is a *dichotomous qualitative nominal variable*. It will be expressed as yes or no.

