 - **Chorioamnionitis:** it is a *dichotomous qualitative nominal variable*. It will be expressed as yes or no.
 - **Premature rupture of membranes** it is a *dichotomous qualitative nominal variable*. It will be expressed as yes or no.
 - **Maternal age:** it is a *continuous quantitative variable*. Measured in years
 - **Maternal size:** it is a *continuous quantitative variable*. Measured in cm.
 - **Cervical surgery:** it is a *dichotomous qualitative nominal variable*. It will be expressed as yes or no.
 - **Congenital uterine anomaly:** it is a *dichotomous qualitative nominal variable*. It will be expressed as yes or no.
 - **Diabetes or gestational diabetes:** it is a *dichotomous qualitative nominal variable*. It will be expressed as yes or no.
 - **Sexually transmitted infection:** it is a *dichotomous qualitative nominal variable*. It will be expressed as yes or no.

- **Smoking during pregnancy:** it is a *dichotomous qualitative nominal variable*. It will be expressed as yes or no.
- **Consuming alcohol or other toxics during pregnancy:** it is a *dichotomous qualitative nominal variable*. It will be expressed as yes or no.
- **Short intragestational period:** it is a *dichotomous qualitative nominal variable*. It will be expressed as yes or no.
- **Extrauterine infection:** it is a *dichotomous qualitative nominal variable*. It will be expressed as yes or no.

All these covariates will be obtained from the clinical history of the mother and the newborn, as all these information will be obtained before the recruitment of the patient in the study. Special importance will be given to the gynaecological clinical history of the pregnancy.

Table 4 - Summary table of variable

	Variable	Type of data	Categories or values
Independent variable	Protocol of invasive mechanical ventilation	Dichotomous qualitative nominal	PSV / ACVGV
Dependent variables	Number of reintubations	Discrete quantitative	Numerical
	Time of weaning	Continuous quantitative	Numerical (days)
Covariates	Sex	Dichotomous qualitative nominal	Men / Women
	Type of preterm	Dichotomous qualitative ordinal	Extremely preterm / Very preterm
	Birthweight	Continuous quantitative	Numerical (grams)
	CPR after birth	Dichotomous qualitative nominal	Yes / No
	5-minute Apgar score	Polychotomous qualitative ordinal	0-3 / 4-6 / 7-10
	Risk factors of prematurity		
	Previous preterm birth	Dichotomous qualitative nominal	Yes / No
	Second trimester miscarriage	Dichotomous qualitative nominal	Yes / No

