7.6 Flow chart

7.7 Data collection

All baseline and outcome data will be collected prospectively using a data collection form. This data form has been designed to collect all clinical and procedural information (see Annex 7) from the different NICUs participating in this project.

Each patient will be identified with a special ID to maintain anonymity, the patient's name cannot appear. Once a week, the neonatologist expert or hospital coordinator of each hospital must collect all the files gathered by the neonatologists of his/her hospital and add them to an online database. When the statistical specialist analyses the database, he/she will not know the name of the baby, or the technique used.

A data quality control service will be contracted to supervise the process and ensure correct data collection.

Period 1: Inclusion and baseline data

The main investigator will contact potential participants to evaluate if they meet all the inclusion criteria and any exclusion criteria. This will take place in the NICU, when there is a preterm infant with NRDS on invasive mechanical ventilation.

If the patient meets all the study criteria, an information form (see Annex 4) and an informed consent (see Annex 5) will be given to the parents after proper explanation.

When the patient is already part of the study, the researcher will proceed with the collection of baseline data, corresponding to the covariates.

Period 2: Intervention period

A baseline researcher, not involved in the outcome assessment, will be responsible for assigning the ID code to each participant. In addition, this

researcher will distribute to the neonatologist the randomised allocation prepared by the biostatistician, indicating the protocol he/she will use.

During the intervention, the baseline researcher must ensure that all dependent variables related to the intervention are collected.

Period 3: Follow up

After 72 hours of the intervention, the baseline researcher not involved in the outcome assessment will evaluate the dependent variable (reintubation).

Once completed, the data form must be sent to the hospital coordinator or neonatologist expert who will add the data to the general online database.

Later, when all the data from all the participants is completed, it will be sent to the statistician expert for analysis.

Figure 18 - Summary of the data collection process

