8.3 Multivariate interference

It will be necessary to do a multivariate analysis adjusting the covariates according to the independent variable with the dependent variables that can interfere in the results, to avoid possible confusion.

Poisson regression model will be used for the association between the intervention and the number of reintubations, which is a **discrete quantitative variable**.

Cox regression models will be used for the association of the intervention with the **time** of weaning, which is a **continuous quantitative variable**. It is calculated as a survival analysis.

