- 6. Formation sessions** (April 2024): An online meeting will be held with the whole team to provide theoretical training on neonatal resuscitation and neonatal mechanical ventilation. Particular emphasis will be placed on invasive mechanical ventilation and weaning. During this meeting, a consensual and detailed document will be sent to the hospital coordinators of each centre with the values of each parameter of the ventilator necessary for both the initiation of weaning and extubation. It will also include the clinical and gasometrical criteria for weaning, extubation and reintubation.

The aim of this training is to homogenise the process and reduce differences in the results between centres.

- 7. Creation of a database** (April 2024): A computer scientist will be hired to create a database, so that the data collected before, during and after the intervention can be correctly recorded.

STAGE 3: Sample recruitment, intervention, and data collection (27 months: May 2024 – July 2026)

8. Sample recruitment: As mentioned above, a consecutive stratified sampling method of extremely and very preterm newborns with NRDS that are on invasive mechanical ventilation, admitted to the NCIU of the participating hospitals will be carried out. Each co-investigator at each centre will be responsible for enrolling patients who meet all the inclusion criteria and any of the exclusion criteria, after the parents or legal guardians have signed the informed consent form (see Annex 5). Each participant will be randomised to one of the intervention groups of the clinical trial. The hospital coordinators of each centre will supervise this process.

Recruitment will continue until each centre has recruited the number of participants assigned by the stratification, with a 1:1 ratio. This is expected to take approximately 26 months (2 years and 2 months).

9. Intervention: During this period, patients will be assigned to one of the protocols for weaning, PSV in one arm of the study and ACVGV in the other.

This process can take a few days or even a few weeks, so an extra month has been added to the projected 26 months for this stage.

10. Follow up: After the intervention, all patients enrolled in the study will be followed for the first 72 hours after extubation, as all clinical data will be recorded in the baby's medical record.

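### Weaning time is analysed as a continuous survival time but recorded only in days, and the data form has no event dates or times

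*Combined protocol and SAP*

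**What the plan says.** Section 7.4 classes weaning time, the secondary outcome, as continuous: "It is counted from the moment the weaning is started until the extubation is executed". Table 4 in the same section gives its values as "Numerical (days", and the form in Annex 7 asks for "Temps de weaning (en dies". The intervention block of that form has only two other fields, the protocol code and a blank field for reintubation. Section 7.7 presents the form as the full collection instrument: "This data form has been designed to collect all clinical and procedural information".

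Section 8.2 assigns Kaplan-Meier to weaning time. Section 8.3 adds: "Cox regression models will be used for the association of the intervention with the" time of weaning. Section 8 names SPSS and says nothing about tied times.

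For the primary outcome, section 7.4 says that "the number of reintubations will be counted for the first 72 hours after the extubation". On duration, section 10.3 says of the weaning intervention: "This process can take a few days or even a few weeks".

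**The concern.** A Cox model works from the order in which infants are extubated. Whole-day recording loses the order within each day. If weaning is short, a large share of the 542 infants would fall on a handful of values, and the estimate then depends on how the software treats ties. The Breslow approximation pulls the hazard ratio toward 1 when ties are heavy. As the plan names no method, a software setting would decide the matter.

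The missing event times also touch the primary outcome. Neither end of the 72-hour window is on the form, so nobody working from the trial database can confirm that a recorded reintubation fell inside it.

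**Working it through.** **The plan's own figure.** The only planned size is for the primary outcome (section 7.3.1): 16% in one group, a difference of 0.10 (reading the printed 0.1 percent units as absolute), two-sided alpha 0.05, power 0.80, dropout 5%. With 16% against 26% and unpooled variance:

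n = (1.960 + 0.842)² × (0.16×0.84 + 0.26×0.74) / 0.10² = 7.849 × 0.3268 / 0.01 = 256.5, so 257; 257 / 0.95 = 270.5, so 271.

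This matches the stated 271 per group and uses nothing about weaning time. The plan gives no hazard ratio, median or power for weaning time.

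**Assumptions needed.** The documents do not supply these: a true hazard ratio of 1.30 for extubation (above 1 means faster weaning), exponential times, medians of 1 to 14 days in the reference arm, rounding up to whole days, 257 evaluable infants per arm, and every infant extubated.

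**Size of the ties.** The share of infants with a recorded time of 1 day at reference median m is the average of 1 − 2^(−1/m) and 1 − 2^(−1.3/m). For m = 1: (0.500 + 0.594)/2 = 55%. For m = 2: (0.293 + 0.363)/2 = 33%. For m = 5: (0.129 + 0.165)/2 = 15%. The simulated shares agree.

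**Effect on the Cox model.** 400 simulated trials per row, each cell showing hazard ratio / power:

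| Median (days) | Largest tie | Exact times | Whole days, Breslow | Whole days, Efron |
|---|---|---|---|---|
| 1 | 55% | 1.31 / 0.84 | 1.19 / 0.51 | 1.29 / 0.82 |
| 2 | 33% | 1.31 / 0.86 | 1.25 / 0.74 | 1.30 / 0.85 |
| 3 | 23% | 1.30 / 0.83 | 1.25 / 0.73 | 1.29 / 0.82 |
| 5 | 15% | 1.30 / 0.81 | 1.27 / 0.77 | 1.30 / 0.81 |
| 7 | 11% | 1.31 / 0.85 | 1.29 / 0.82 | 1.31 / 0.85 |
| 14 | 6% | 1.31 / 0.85 | 1.30 / 0.84 | 1.31 / 0.85 |

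The Breslow power losses down the table are 33, 12, 10, 4, 3 and 1 points.

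**Repeat runs.**
- With 271 per arm and 300 trials per setting, Breslow gave 1.19 (power 83% to 51%), 1.24 (86% to 72%), 1.26 (87% to 81%) and 1.27 (88% to 83%) at medians of 1, 2, 3 and 5 days.
- A further set at 257 per arm gave 1.19 (0.83 to 0.52), 1.23 (0.80 to 0.67) and 1.28 (0.83 to 0.80) at 1, 2 and 5 days. In that set, times recorded to the hour recovered the exact-time result even with Breslow.
- The Monte Carlo standard error of a power near 0.8 from 400 trials is √(0.8×0.2/400) = 0.02, so single percentage points should not be read closely.

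**Sensitivity.**
- Times less spread out (Weibull, shape 1.5) make Breslow worse: power 0.82 to 0.29 at a 1-day median, 0.84 to 0.62 at 2 days, 0.82 to 0.75 at 5 days. Efron then also loses at 1 day (hazard ratio 1.26, power 0.82 to 0.72), but about 1 point or less from 2 days.
- With a true hazard ratio of 1.50, Breslow gives 1.29, 1.39, 1.42 and 1.46 at 1, 2, 3 and 5 days. Power stays at 0.92 or more, so the harm there is to the estimate.
- With no true effect and a 2-day median (1,000 trials), the estimate is unbiased. The rejection rate is 0.03 with Breslow and 0.06 with exact times or Efron.

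**The case against.** The strongest reply is that the material loss needs several unstated conditions together: whole-day entry, short weaning and Breslow ties. That is correct. The form fixes a unit, not a precision, and decimal days would fit both Table 4 and Annex 7. Section 10.3 allows for weeks as well as days, and nothing in the plan points to a 1-day median. The background remark "Some infants require a very short period of ventilation" concerns total ventilation, not weaning under this trial's criteria. No planned power is lost either, since only the primary outcome was sized.

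A reader might also infer three stronger points that the documents do not support:
- That the 72-hour window is unverifiable. Section 10.3 says the clinical data of the follow-up will be in the infant's medical record, so it can be checked at source.
- That reintubation is captured as yes or no. The field is blank with no response format, and Table 4 defines a numerical count.
- That most infants will wean within a few days, making heavy ties certain. Section 10.3 does not say so.

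What stands is the mismatch itself: a continuous definition, a unit of days, no event times on the form, and no rule for ties.

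**Conclusion.** The concern holds as a cheap improvement to data collection and to one line of the analysis plan. If days are whole numbers, the true hazard ratio is 1.30, times are exponential and ties are handled by Breslow, the estimate shrinks to about 1.19 at a 1-day median, 1.23 to 1.26 at 2 to 3 days and 1.27 to 1.29 at 5 to 7 days. The matching power losses are 31 to 33, 6 to 14 and 3 to 5 points. They are larger if times are less spread out than exponential. With Efron the loss is about 1 point or less from a 2-day median. The median, hazard ratio, distribution, rounding and tie method are all assumptions.

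The effect is confined to the secondary outcome and works against finding a difference; the run with no true effect showed no excess of false positives. For the primary outcome, the consequence is that the 72-hour window cannot be derived or checked from the trial dataset, though it can be from the medical record. The 271 per group is unaffected.

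**What to change.** In Annex 7, replace the days field with the date and clock time of weaning start, of extubation and of each reintubation. Derive weaning time in hours, and the count of reintubations within 72 hours of extubation, from these entries. Change the unit in Table 4 to hours. In section 8.3, name Efron for any ties that remain. Naming Efron alone would repair most of the loss, but not fully at very short weaning times, and it would not make the 72-hour window checkable.

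The cost is a few more fields per infant. Doing it before recruitment avoids going back to as many as 542 records in five hospitals to recover the times.
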